- Following 3 months of lifestyle modification and intensive therapy if weight loss <5% Olistat will be introduced
- At 6 months participants will be referred to self-management program for ongoing behaviour modification
- For relevant cases at 12 months if weight loss not <5% and pathology demonstrates ketosis referral for surgical review
- Bariatric surgical assessment and patient counselling will be provided to determine:
 - whether surgery is indicated;
 - the patient's desire for, and likely tolerance to surgery; and
 - if so, what surgery type is most appropriate for the patient (Nguyen, 2013).

Following the completion of the up to 24 month program (the intervention) participants (both intervention and control) will be invited to continue to be part of the research project by way of providing follow-up data to determine sustainability of the intervention and project. Given Participants are existing patients of the service and will continue to be review as part of routine care at the Diabetes Centre, at their 24 month collection point (intervention and control) participants will be invited to continue with a collection of indicated markers at 6 and 12 months post intervention. If at their last visit (24 months) the participant indicates that they are happy for this to occur this verbal consent will be recorded on the spreadsheet used to collect project data – ie consent given: yes and date. If consent is provided by the participant, ongoing data will be collected following intervention period at 6 and 12 months post intervention.

Intervention Clarified/Differences in two arms of Study TSRAC QUESTION 12 (Response)

- Intervention of interest – **individualised** multidisciplinary multi-intervention assessment and treatment
- The impact of a model of care that assesses, triages and treats **all** factors impacting on metabolic processes from point of entry

Differences in two arms	
Control Group	Intervention Group

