
 1. Patient attends Diabetes Clinic 2. Pre-assessment includes physical measurements (BMI, BP) and HbA1c by CDE. Plus; Psychological Distress PHQ-9 and GAD-7, QoL SF-36v2, Assessment of Quality of Life (AQoL) and Work Productivity and Activity Impairment (WPAI). The above data will be collected by a research assistant and not the clinicians to prevent impact of 'treatment as usual'. 3. Patient reviewed by endocrinologist and management is diabetes and endocrine focused 4. Screening may include HbA1c, lipids, vitamin B12 and folates, TFTs, LFTs, ACR, eGFR 5. Referral to diabetes educator as needed for ongoing education if HbA1c above target 6. Referral to psychologist as required if patient raises psychosocial problems during consultations with either CDE or endocrinologist 7. Referral to dietitian if HbA1c > 9% in type 2 diabetes 8. Adhoc referral for bariatric assessment if BMI >40 and failed attempts at weight loss 	
 1. Patient attends AMOS Clinic 2. (a) Pre-assessment includes physical measurements (BMI, BP, girth) and HbA1c by CDE. (b) Universal screening - completion of scales to support planned assessment and care: 
 • Psychometric (Psychological Distress PHQ-9 and GAD-7, QoL SF-36v2 and AQoL, WPAI) • Epworth Sleepiness Scale • Absolute cardiovascular risk • Edmonton Obesity Staging (c) Review with physiotherapist for: 
 • Assessment for physical functioning performed • Completion of McCaffery Pain Assessment scale 3. (a) According to psychometric scales patient is triaged into psychologist for 1:1 or group session (b) Patient booked into physiotherapist for 1:1 or group sessions (c) According to dietitian assessment patient seen 1:1 or booked into group program (program facilitated by psychologist and dietitian with focus on identification of barriers) 4. Patient reviewed by endocrinologist and management is diabetes/endocrine and obesity focused 5. Screening for metabolic pathology request provided as per control group with addition of leptin and ketones (to identify weight loss and ketosis) and vitamin D In addition, assessment and review by dietitian to support development of treatment plan. 6. Treatment Plan agreed: 
 • Weight Loss goals determined • Referral as relevant to: 
 ○ Other health professional/specialist (sleep apnoea or pain management assessment if applicable) ○ Community Based Weight /Pain management programs (Stanford - GTMOL, OPAL) • Resistant or balance training • Medicines alteration and/or titration • Behaviours Modification and Self-Maintenance awareness 7. Initiation of Orlistat if BMI > 35 and < 2% weight loss after 3 months 8. Referral for bariatric assessment if deemed suitable and after 12 months failed treatment.

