- “The Australian Clinical Practice Guidelines for the Management of Overweight and Obesity in Adults” (NHMRC, 2013) provide an evidence-based, stepped approach to obesity management. The first level of management is lifestyle intervention, comprising exercise, nutrition and psychological intervention. The second level of management is medication management. The third level of management is surgery. The guidelines consider that higher levels of management are indicated when lower levels of management have been insufficient to achieve desired clinical outcomes. This is the management approach the hospital research team will adopt in their patient management strategies.
- However, the control group in this study will receive ‘usual care’. The research team is aware this means patients in the intervention or control groups may receive lifestyle, medication and / or surgical management through alternative clinical pathways (e.g. through primary care, private hospital or other sources of clinical support). This is usual in obesity clinical trials with a ‘usual care’ control arm (see the Australian Clinical Guidelines discussion on this). Consistent with other obesity studies, we will account for any differences post-hoc in our data analysis.

AMOS Research Project Participant Flow Chart

Study Duration/Timelines:

Stage 1: Recruitment of participants to study and informed consent (0 – 3 months)

Stage 2: Data collection, referral to therapies (3 – 12 months)

Stage 3: Ongoing recruitment and informed consent (6 – 9 month)

Stage 4: Initial data analysis (15 months)

Stage 5: Data Analysis and Interpretation (24-26 month)

Stage 6: Presentation and publication (15 and 26 month)

Study Population

Participants

Inclusion Criteria

- Person with BMI >30 with waist circumference \geq 88cms in women and \geq 102cms in men
- Those aged < 75 years of age
- Patient has diabetes mellitus
- Already in the care of the North West diabetes service
- Able to provide informed consent
- Not pregnant or breastfeeding

Exclusion Criteria

- Person with diabetes with a BMI > 30 with waist circumference < 88cms in women and <102cms in men
- Person with diabetes with a BMI \leq 30
- Those aged \geq 75 years of age
- Any pregnant or breastfeeding person with diabetes
- Any person with diabetes < 18 years of age
- Any person with a cognitive impairment, an intellectual disability or uncontrolled psychotic illness

Lay Description of Participation

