This study looks at the effects of care that is tailored to obesity. Patients invited to the study will be told about what they will need to do if they decide to be involved. They will be asked to provide written consent before being placed at random to the treatment group or normal care. Participants in the control group will receive routine care as part of the normal Adult Diabetes Clinic. Participants in the intervention group will complete a number of hand written assessments about sleep, pain, stress and/or how they have been feeling. Some measurements of body shape will be taken as well as some blood tests each 6 months. Some of these are routine tests for normal care and others are specific to the study. All participants will attend the service each 3 months – that is 4 times per year – these visits may last 30 to 90 minutes. At these times they may see other health professionals such as a physiotherapist, psychologist or dietitian – this will be on an individual basis at first and then may be in a group format. The group programs will involve learning about ways to stop the cycle of obesity and/or some physical activity. If no weight loss is achieved a dose of Orlistat will be suggested for a 3 month period. The participants will be contacted by the research assistant to arrange a time for their follow-up visits and to see how they are doing overall. If suitable and willing the participants may be referred to see a surgeon to discuss other options.

Nature of Existing Relationships between Potential Participants/Research team and Voluntary Consent

A majority of the participants will have had a past and/or current relationship with a number of the health professionals involved in the research study group. Potential participants will be clearly informed that their relationship with any of the investigations or staff involved in their medical care will not be influenced by their choice to participate or not to participate.

Potential participants will be assured that the decision to participate is voluntary and will have no influence on their relationship with medical or allied health professional staff, the research team or the THO-North West.

Impact of the research on the Relationship between Participants and the Researcher

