Our study aims to look at the effects of care that is tailored specifically to obesity. The study involves complete several hand written assessments about sleep, pain, stress and/or how they have been feeling. If you need assistance with this we will provide this. Also some measurements of your body as well as some blood tests each 6 months. Some of these are routine tests for normal care and others are specific to the study. You will visit the clinic each 3 months – that is 4 times per year – these visits may last 30 to 90 minutes. At these times you will see other health professionals such as a physiotherapist, psychologist or dietitian – this will be on an individual basis at first and then may be in a group format. The group programs will involve learning about ways to stop the cycle of obesity and/or some physical activity. You can discuss these options with the staff member at the time – you will not be forced to go into any specific treatment. If no weight loss is achieved a dose of Orlistat will be suggested for a 3 month period. If after 12 months weight loss is still low and you are interested, you may be referred to a surgeon to discuss other options."

Given participants are existing patients of the service and will continue to be review as part of routine care at the Diabetes Centre, at their 24 month collection point (intervention and control) they will be invited to continue with a collection of indicated markers at 6 and 12 months post intervention. If at this last visit they indicate that they are happy for this to occur this verbal consent will be added to the spreadsheet used to collect the project data – ie consent given: yes and date.

Would knowledge of recruitment, participation or exclusion Expose the Person to Disadvantage or Risk

No

Seeking Consent

- Potential participants are identified through records of patients with BMI >30 via DiaBASE program (clinical software program) in order of last review
- Participants will be screened for eligibility by the Research Assistant after this list is generated
- We will use a random number generator to assign patients to groups
- After an initial notification that the individual has been identified as a potential participant for the study on their next appointment letter the Research Assistant will invite the potential participant to be involved in the study
- The research assistant will have had previous training in seeking informed consent

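### The protocol gives two incompatible 3-month triggers for orlistat, and its 12-month surgical-referral condition is reversed as written

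*Protocol*

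**What the plan says.** **Orlistat at 3 months.** The protocol states the trigger in four places.

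- Methodology, Study Intervention: "Following 3 months of lifestyle modification and intensive therapy if weight loss <5% Olistat will be introduced". No BMI condition is attached.
- The section headed "Intervention Clarified/Differences in two arms of Study", comparison table, intervention column, item 7: "Initiation of Orlistat if BMI > 35 and < 2% weight loss after 3 months".
- Lay Description of Participation: "If no weight loss is achieved a dose of Orlistat will be suggested for a 3 month period".
- Advertisement of the Study (telephone script): the same sentence as in the lay description. The script also tells the listener that "you will not be forced to go into any specific treatment".

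Two other passages bear on the BMI condition. The inclusion criterion begins "Person with BMI >30 with waist circumference", so people with BMI above 30 and up to 35 can be enrolled. The section Orlistat and Other Weight Loss Medication cites a guideline floor of BMI 30.0 for prescribing the drug.

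**Surgical review at 12 months.** Study Intervention says: "For relevant cases at 12 months if weight loss not <5% and pathology demonstrates ketosis referral for surgical review". Item 8 of the intervention column says: "Referral for bariatric assessment if deemed suitable and after 12 months failed treatment". The telephone script mentions a surgeon for people whose loss remains small after 12 months. The section on orlistat and bariatric surgery sets out the stepped principle that the team will follow: move up a level when the level below has not done enough.

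**The concern.** Both orlistat rules apply to the same arm at the same decision point, and each is a fixed numeric threshold. A clinician following Study Intervention and one following the table would treat some participants differently, and both would be following the protocol.

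The surgical condition raises a separate problem. Taken literally, it sends those who responded to the programme for surgical review and leaves out those who did not.

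Orlistat and surgical assessment are escalation steps of the model under test. Management of Cross Contamination names both when it explains how the arms are kept apart, and body weight is a primary outcome. The protocol also expects the trial to yield decision algorithms for surgical referral and a model that other health organisations could adopt. At stake are who in the intervention arm is offered each step and whether the model can be delivered and replicated from the text.

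**Working it through.** The main check is logical: apply each rule as written to the same participant.

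**Step 1. Orlistat at 3 months.** Inputs are the Study Intervention rule (loss <5%, any BMI), the table item 7 rule (BMI >35 and loss <2%) and the entry criterion (BMI >30).

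| BMI | Loss at 3 months | Study Intervention | Table item 7 |
|---|---|---|---|
| >30 to 35 | <2% | orlistat | no |
| >30 to 35 | 2% to <5% | orlistat | no |
| >35 | <2% | orlistat | orlistat |
| >35 | 2% to <5% | orlistat | no |
| any | 5% or more | no | no |

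The item 7 group is a strict subset of the Study Intervention group. The rules agree in two rows and disagree in three. The disagreement covers everyone who loses 2% to <5%, plus those with BMI >30 to 35 who lose <2%.

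**Step 2. The guideline floor.** The cited floor of BMI 30.0 is met at entry by every participant, because entry requires BMI >30. It is compatible with having no further BMI limit and is wider than item 7's >35. It says nothing about a 3-month weight-loss threshold, so it does not settle which rule applies.

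**Step 3. The plain-language wording.** Take a participant with BMI 36 and a 1% loss. Both clinical rules give orlistat (1 <5; 36 >35 and 1 <2). The lay sentence, read strictly, does not, because some weight was lost. So that sentence matches neither rule exactly.

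**Step 4. Surgical review at 12 months.** Not (loss <5%) is the same as loss of 5% or more. A 6% loss meets the weight condition; a 1% loss does not. Against this:

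- item 8 requires that treatment has failed;
- the telephone script requires that the loss is still small;
- the stepped principle requires that the lower level was insufficient;
- the control column's ad hoc bariatric referral also follows failed attempts at weight loss.

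All four point to small losses. The Study Intervention line stands alone in the other direction.

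**Step 5. Ketosis.** Study Intervention adds ketosis as a condition for surgical review. Item 8 does not mention it. Correcting the inequality alone would therefore leave the two statements different.

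**Step 6. Does any planned figure depend on this?** The sample size uses d = 0.5, significance level 0.05 (two-sided assumed) and power 0.95: n per arm = 2 × (1.960 + 1.645)² / 0.5² = 2 × 12.996 / 0.25 ≈ 104. The t-based version gives 105, against the 106 stated. Neither trigger enters the calculation, so it stands whichever rule is chosen.

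**The case against.** **The table governs.** Its section heading presents it as a clarification, which is a reasonable basis for treating it as the operative text. That part stands. But no passage says that it replaces Study Intervention, where introduction of the drug is worded as mandatory. Neither text is an amendment log.

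**Care is individualised and optional.** The plan is agreed with the patient, orlistat is only suggested in the lay texts, and no treatment is forced. This limits the consequence, since qualifying for orlistat is not the same as taking it. It does not reconcile two different fixed thresholds.

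**The surgical line is an obvious slip.** The intended direction is clear from the other passages, the line is limited to relevant cases, and a surgical assessment follows. Few readers would act on the literal text. The line is still wrong and should be corrected.

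**Stronger readings that the documents do not support.**

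- A reader might infer that participants are misinformed. The lay description and script are plain-language summaries, not prescribing rules. The consent pages were removed from the text available for review, so what participants are told overall cannot be judged.
- A reader might want a count. If 3-month loss were normal with mean 1% to 4% and SD 2% to 4%, the share between 2% and 5% would run from 0.243 (mean 1, SD 4) to 0.547 (mean 3.5, SD 2), or about 26 to 58 of 106. The protocol supports neither the shape nor the parameters, so this range reflects the assumption and is not a finding.
- A reader might convert that share into a shift in mean weight using the 2 kg orlistat effect quoted in the effect-size justification. That is a 12-month estimate, the lay texts describe a 3-month course, and uptake is unknown.
- The BMI >30 to 35 group cannot be sized either. The background section gives a clinic mean BMI of 44.5, which suggests that the group may be small, but no spread is given.

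**Conclusion.** The protocol is wrong as written on two treatment decisions in the intervention arm. The two orlistat triggers cannot both be followed for eligible participants who lose 2% to <5%, or who have BMI >30 to 35 and lose <2%. The surgical-review condition in Study Intervention is the reverse of what the rest of the protocol requires. Both conclusions follow from the text and need no assumption.

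The consequence is limited to who is offered orlistat and surgical review and to how reproducible the model of care is. The randomised comparison and the sample size are unaffected. The documents do not allow the number of affected participants, or any effect on weight, to be sized. Which orlistat threshold is clinically right is for the investigators to decide.

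**What to change.** - **Orlistat.** State one rule, with its weight-loss threshold and any BMI floor, identically in Study Intervention and in table item 7. If the clarification section is meant to govern, that rule is item 7. In choosing, note that the protocol's cited guideline floor is BMI 30.0, which every participant meets at entry, so the >35 limit is a deliberate narrowing that should be stated as such.
- **Plain-language texts.** Reword the orlistat sentence in the lay description and the telephone script so that it is consistent with the chosen rule.
- **Surgical review.** In Study Intervention, change the condition so that review follows when 12-month weight loss is <5%.
- **Ketosis.** State whether this condition applies, and make Study Intervention and item 8 agree. If it is meant to be part of being deemed suitable in item 8, say so.

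The cost is a wording amendment, with no added visits, procedures or participants. If the wider Study Intervention rule is chosen, more orlistat may be needed. The drug is not listed on the Pharmaceutical Benefits Scheme, and the health organisation has approved interim funding for it, so supply should be checked before that choice is made.

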Again although weight management is an important issue in the care of people with type 2 diabetes it is not the focus of the clinic; basic advice is provided in diet and physical activity by diabetes educators. Limited state funded dietetic services are utilised in the care of paediatrics with diabetes and generally adult individuals with type 1 and some with type 2 with pre-existing co-morbidities. Individuals with weight issues who are referred to state funded dietetic services for individualisation of advice are presented with a letter indicating that they ‘are not likely to be seen so will not be placed on a wait list’ and a list of private dietitians is provided. The same issue prevails as listed above in relation to financial capacity of the individuals. Thus, the majority of people with type 2 diabetes without co-morbidities or co-morbidities that are controlled, will not have personalised calculations of energy requirements needed and specific advice on the particular caloric decreased required to provide weight loss. In addition, the reasons behind eating behaviour and weight gain are more often from a psychology basis and/or related to funding of differing food types. Another limited health professional resource in the north west.

Methodology *(continue)*

Management of Cross Contamination TSRAC QUESTION 3 (Response)

- Randomisation will be achieved by method listed above
- Cross contamination is managed by several means:
 - The clinics are run on alternate days – thus patients are unlikely to come across each other – they may within the community as they would with any other RCT
 - The interventions which include multidisciplinary assessment and care, the use of orlistat and potentially bariatric surgery if identified as a suitable candidate requires assessment and referral – the control group patients will not have the assessments performed routinely and/or be in the setting to have these referrals created
 - The intervention group utilises a different credentialled diabetes educator than the ones used in the traditional (usual care) diabetes clinic
 - The endocrinologist involved in this study will mainly be involved in the AMOS clinic – during other clinics he will be seeing patients with type 1 diabetes of lower BMI who do not meet the criteria and due to different disease process their needs will differ
 - An alternate endocrinologist not involved in AMOS will see the control group within the traditional (usual care) diabetes clinic

Timing of Assessment Scales TSRAC QUESTION 4 (Response)

- Psychometric and pain measurements will be taken at the same intervals; baseline, 6,12,18,24 months
- Both will be taken on the same day – however, by a different health professional. The only reason for this is that pain assessment falls into a normal assessment for physiotherapists

Orlistat and Other Weight Loss Medication TSRAC QUESTION 10 (Response)

- The use of Orlistat is drawn from recommendations draw from the NICE and NHMRC guidelines for management of obesity.
- Orlistat is currently the only medication registered for use in treating overweight (with comorbidities) and obesity that has been evaluated for long-term safety. Although it is listed on the Repatriation Pharmaceutical Benefits Scheme, it is not listed on the Pharmaceutical Benefits Scheme (PBS). Data suggest that it is more cost-effective in individuals who have numerous comorbidities (type 2 diabetes, hypertension, hypercholesterolaemia)
- Orlistat should be prescribed only as part of an overall plan for managing obesity in adults who hold a BMI of 30.0kg/m² or more (NHMRC 2013).
- The decision to use drug treatment in non- Repatriation clients for longer than 3 months and to a maximum of 6 months (usually for weight maintenance) should be made after discussing potential benefits and limitations with the patient.
- The co-prescribing of orlistat with other drugs aimed at weight reduction is not recommended (NHMRC 2013).
- Other medications found to support weight loss include;

“sibutramine (Horvath et al. 2008), rimonabant (Curioni & André 2006; Nissen et al. 2008; van Gaal et al. 2008), taranabant (Proietto et al. 2010), metformin (Knowler et al. 2009) and

lorcaserin (Smith et al. 2010). However, many of these medications have been associated with adverse effects and have been withdrawn (e.g. sibutramine) or were never approved (e.g. rimonabant, taranabant) in Australia. The evidence on the effects of weight loss medications on health outcomes other than weight loss is limited.” (NHMRC 2013)

[figure not shown]
- Phentermine is registered for use as a short-term (e.g. 3-month) adjunct to dietary management of obesity, under medical supervision. The use of Phentermine is not likely to be utilised within this clinic as it is associated with a range of side effects (e.g. hypertension, tachycardia, insomnia) that is problematic with the patient cohort and their existing co-morbidities and its long-term safety has not been tested (NHMRC 2013). Further, it is not listed on the PBS.
- All patients will be screened for medications that they are taking (including complementary drugs) and this will be reviewed against those that have been prescribed as part of a normal medical assessment.

Orlistat as the Pharmaceutical Intervention and Bariatric Surgery

TSRAC QUESTION 11 (Response)

- Orlistat is being used for the reasons mentioned above; evidence supports its use in obesity management as it reduces the absorption of energy-dense fat by inhibiting pancreatic and gastric lipases.
- In conjunction with lifestyle intervention, orlistat is associated with slight reductions in systolic and diastolic blood pressure (Padwal et al. 2003), modest weight loss in adults with comorbidities, including metabolic syndrome (Svendson et al. 2009), hypertension (Siebenhofer et al. 2009) and type 2 diabetes (Jacob et al. 2009; Norris et al. 2005) and slight improvement in glycaemic control (Jacob et al. 2009; Norris et al. 2005) in adults with type 2 diabetes with no adverse effects on lipid profile (Eliasson et al. 2007; Norris et al. 2005). (NHMRC 2013).
- Orlistat is not PBS listed and will not be offered to the control group.
- Referral for lapbanding will only be offered to the ‘control’ group by the research team if the patient has a BMI of >40, has presented for therapies planned for behaviour change and has had failed attempts at weight loss following this.
- “The Australian Clinical Practice Guidelines for the Management of Overweight and Obesity in Adults” (NHMRC, 2013) provide an evidence-based, stepped approach to obesity management. The first level of management is lifestyle intervention, comprising exercise, nutrition and psychological intervention. The second level of management is medication management. The third level of management is surgery. The guidelines consider that higher levels of management are indicated when lower levels of management have been insufficient to achieve desired clinical outcomes. This is the management approach the hospital research team will adopt in their patient management strategies.
- However, the control group in this study will receive ‘usual care’. The research team is aware this means patients in the intervention or control groups may receive lifestyle, medication and / or surgical management through alternative clinical pathways (e.g. through primary care, private hospital or other sources of clinical support). This is usual in obesity clinical trials with a ‘usual care’ control arm (see the Australian Clinical Guidelines discussion on this). Consistent with other obesity studies, we will account for any differences post-hoc in our data analysis.

AMOS Research Project Participant Flow Chart

Study Duration/Timelines:

Stage 1: Recruitment of participants to study and informed consent (0 – 3 months)

Stage 2: Data collection, referral to therapies (3 – 12 months)

Stage 3: Ongoing recruitment and informed consent (6 – 9 month)

Stage 4: Initial data analysis (15 months)

Stage 5: Data Analysis and Interpretation (24-26 month)

Stage 6: Presentation and publication (15 and 26 month)

Study Population

Participants

Inclusion Criteria

- Person with BMI >30 with waist circumference \geq 88cms in women and \geq 102cms in men
- Those aged < 75 years of age
- Patient has diabetes mellitus
- Already in the care of the North West diabetes service
- Able to provide informed consent
- Not pregnant or breastfeeding

Exclusion Criteria

- Person with diabetes with a BMI > 30 with waist circumference < 88cms in women and <102cms in men
- Person with diabetes with a BMI \leq 30
- Those aged \geq 75 years of age
- Any pregnant or breastfeeding person with diabetes
- Any person with diabetes < 18 years of age
- Any person with a cognitive impairment, an intellectual disability or uncontrolled psychotic illness

Lay Description of Participation

This study looks at the effects of care that is tailored to obesity. Patients invited to the study will be told about what they will need to do if they decide to be involved. They will be asked to provide written consent before being placed at random to the treatment group or normal care. Participants in the control group will receive routine care as part of the normal Adult Diabetes Clinic. Participants in the intervention group will complete a number of hand written assessments about sleep, pain, stress and/or how they have been feeling. Some measurements of body shape will be taken as well as some blood tests each 6 months. Some of these are routine tests for normal care and others are specific to the study. All participants will attend the service each 3 months – that is 4 times per year – these visits may last 30 to 90 minutes. At these times they may see other health professionals such as a physiotherapist, psychologist or dietitian – this will be on an individual basis at first and then may be in a group format. The group programs will involve learning about ways to stop the cycle of obesity and/or some physical activity. If no weight loss is achieved a dose of Orlistat will be suggested for a 3 month period. The participants will be contacted by the research assistant to arrange a time for their follow-up visits and to see how they are doing overall. If suitable and willing the participants may be referred to see a surgeon to discuss other options.

Nature of Existing Relationships between Potential Participants/Research team and Voluntary Consent

A majority of the participants will have had a past and/or current relationship with a number of the health professionals involved in the research study group. Potential participants will be clearly informed that their relationship with any of the investigations or staff involved in their medical care will not be influenced by their choice to participate or not to participate.

Potential participants will be assured that the decision to participate is voluntary and will have no influence on their relationship with medical or allied health professional staff, the research team or the THO-North West.

Impact of the research on the Relationship between Participants and the Researcher

Some potential participants will be in a doctor/allied health – patient relationship with one or more of the researchers. However, these researchers will not be involved in the mentioning of the study to the potential participants – they will be referred to the research assistant/case manager for a fuller explanation of the study and to gain informed consent. They will be assured that participation or not is entirely their decision and will not affect their relationship with any member of the health team in any way.

Male to Female Ratios

It is expected that recruitment of male to female ratios will generally be fairly similar. There may be a higher intake of females as they are more likely to access health care services than males. The male population has a slightly higher rate of obesity than females. Diabetes is of similar proportion across both genders.

Considerations for Vulnerable Groups

THO North West provides routine clinical services to people from backgrounds whose language is other than English, people in existing dependent / unequal relationships and Aboriginal and / or Torres Strait Islander (ATSI) peoples.

The hospital has liaison officers for people from Culturally and Linguistically Diverse (CALD) backgrounds, including ATSI peoples. Staff providing the clinical services being delivered in this project have received training in cultural competence. Staff have access to translation and interpreter services which will be used to assist in communicating with participants if required.

Data Management and Statistical Analysis

Data Management

- Data will be collected as part of the normal process of the clinic in the DiaBASE program (clinical software program)
- The DiaBASE can only be accessed by relevant clinicians for entry of information only
- Once data is required for analysis a report will be exported from DiaBASE onto Excel
- Data will be reviewed for accuracy and completeness by the Co-Principal Investigator with role of project management on a quarterly basis.
- Gaps in data will be addressed through the Co-PI and the Research Assistant (Case Manager)
- Staff of the THO are bound by rules of confidentiality in relation to patient information

Statistical Analysis

Sample Size TSRAC Q5

- The sample size of 212 participants (randomising 106 participants to each group) was calculated by performing power calculations assuming significant differences between intervention and control groups in one or more of the following measures:
 - HbA1c
 - Absolute cardiovascular risk
 - Psychometric measures (PHQ-9, depression and SF-36 Quality of Life)
 - Decline in Edmonton Obesity status (Padwal, 2011)
- Rationale - the power is in general a function of the possible distributions under the alternative hypothesis. As the power increases, the chances of a Type II error occurring decrease. We conducted power calculations to calculate the minimum sample size required using a target variance for an estimate to be derived from the sample eventually obtained.
- We assumed a Cohens d of 0.5 and a power of 0.95 based on estimates in the peer-reviewed literature.
- We assumed significance criteria of 0.05, the probability of the data implying an effect at least as large as the observed effect when the null hypothesis is true must be less than 0.05, for the null hypothesis of no effect to be rejected.
- Further, this assumed:
 - A follow-up period of at least 6 months for each participant.
 - Not all participants will be cared for simultaneously – there will be multiple intakes e.g. as people exit the program enrol new participants and controls.

Analysis TSRAC Q12

- Data will be exported from DiaBASE (Clinical software program) and entered into Excel (Microsoft) for data cleaning, then imported into Stata 12 and SPSS for analysis.
- Analysis will be performed using SPSS and Stata.
- Descriptive statistics will first be calculated to investigate the proportions of categorical variables and the distribution of continuous variables.
- Pearson's chi-square test or Fisher's exact tests will be utilized for investigation of associations between categorical variables, while independent t-tests will be used to investigate differences in continuous data between the control and intervention groups.
- For dichotomous outcomes logistic regression will be performed.
- For continuous outcome data analysis of covariance will be performed to test the effects of predictor variables.
- Adjusted relative risks (aRR) of metabolic and psychometric outcomes will be calculated for the control vs. intervention groups (with 95% confidence intervals) using a Poisson regression model with robust error variance.
- The regression models will include adjustment for age, pre-existing diabetes, socio-economic status and Asian or indigenous ethnicity.

Please provide additional justification on for the effect size with references.

The main body of evidence in support of the effect size was the National Health and Medical Research Council (2013) *Clinical practice guidelines for the management of overweight and obesity in adults, adolescents and children in Australia - Systematic Review*. Melbourne: National Health and Medical Research Council. This systematic review was written by [name] who is also now part of the research team.

There is substantial heterogeneity in the literature regarding the effects of obesity management on patients with type 2 diabetes. Further there is a proximal link between biomarkers for CVD and cancer (the intermediate endpoints in our study) that, although well proven, does not describe well but the timeframe between biomarker changes and outcomes is poorly described.

We have therefore chosen to estimate a moderate effect size (Cohens d 0.5) and accept that in doing so, some outcomes measures may not demonstrate significant between group differences.

Although many trials conducted in patients with obesity and type 2 diabetes generally demonstrate minimal weight loss with weight regain occurring within short timeframes, there are varying lead times between when weight is lost and when differential cardiovascular outcomes (in particular) are observed.

References used: Impacts of weight loss interventions in type 2 diabetes

Glycaemic control

Results from the following studies demonstrate a high degree of variability in the impact of weight reduction interventions on glycaemic measures. Cohens d of 0.5 for effect size was selected to balance differences observed across meta-analyses.

Norris et al. (2005a) conducted a meta-analysis of 22 RCTs involving 4,659 participants over up to 5 years that assessed the impact of non-pharmacological weight loss interventions on type 2 diabetes. Estimates were pooled for any intervention versus usual care, very low calorie diet (VLCD) versus low calorie diet (LCD) and physical activity versus no or less intensive physical activity. Weight losses of up to 12 kg were achieved with lifestyle interventions. Weight losses of approximately 3 kg (95% CI, -0.5 to 6.4) were achieved with diet versus usual care. The corresponding decrease in HbA1c was approximately 0.7% across these studies. More intense physical activity was associated with greater weight reduction but not with greater reductions in HbA1c.

